	Voluntary Services/Teams as appropriate
Ambulance service/Paramedic practitioner	Palliative Care Nurses
Making connections coordinator	Learning Disability Practitioner
Dementia practitioner	Substance Misuse Service
Pharmacist	Therapists (Physiotherapy, occupational therapy, speech and language)
	Continuing care
	Complex care pathways

Source: NEHF CCG and Happy, Healthy, at Home Vanguard

Once a patient has been referred to the ICT, they are discussed at the following ICT meeting to determine the best plan of action and the most appropriate point of contact within the team. A patient may be seen by a member of the team before this first multidisciplinary team meeting. When appropriate, the teams organise prompt visits from specialists to a person's home, for example for dementia assessments or podiatry appointments. Where these visits are done by professionals normally working in outpatient clinics, they are logged in the SUS data as outpatient attendances. However, community appointments are not documented in the SUS data, independent of whether these occur at a patient's home or at a clinic.

In the earlier stages of the programme, patients were discharged from the ICTs when they were deemed no longer in need of the ICT. However, often these patients would be re-referred to the ICTs at a later date. Now patients referred to an ICT are considered to stay on the ICT register in perpetuum, although differentiation is made between active and dormant patients.

One of the aims of the PACS was to create a shared care record, so that patients need only 'tell their story once'. However, due to both technology and information governance issues, this has not yet been made possible. Nonetheless, information about patients from various sources is shared verbally during the ICT meetings.

[figure not shown]
Information from ICT meetings is held on a separate ICT database (not available to the IAU). Information on whether a patient is being seen by an ICT is not routinely shared with hospital staff. The ambulance service may know if a patient is being seen by an ICT if the patient has a care plan. In such cases, if appropriate, the ambulance service would contact the ICT paramedic who would visit the patient and see if other support or services would be more appropriate.

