Appropriate baseline variables will be included in both the matching and the regression models. All baseline variables are calculated on pre-period data. Potential baseline variables to include in the matching or as covariates in the modelling are listed in Table 3.

Table 3. Potential baseline variables

Category	Variables at patient level
Demographics & socio-demographics	
 • Approximate age at index date • Gender • Ethnicity • Average socioeconomic deprivation deciles, based on the Index of Multiple Deprivation (IMD) 2015, available at layer super output area (LSOA) level • Urban/rural classification at lower LSOA level, based on the 2011 census
Prior hospital use	
 • Number of emergency admissions in the last 60 days of the pre-period • Number of emergency admissions in year -1, the last year of the pre-period (i.e. 365 to 1 day before index date) • Number of emergency admissions in year -2 of the pre-period (i.e. 730 to 366 days before index date) • Number of ACS emergency admissions in the last 60 days of the pre-period • Number of ACS emergency admissions in year -1 of the pre-period • Number of ACS admissions in the year -2 of the pre-period • Number of elective admissions in year -1 of the pre-period • Number of A&E attendances in year -1 of the pre-period • Number of outpatient attendances in year -1 of the pre-period • Number of missed outpatient visits in year -1 of the pre-period • Average length of stay in year -1 of the pre-period
Health variables	
 • Elixhauser list of comorbidities, identified in the pre-period • Specific comorbidities linked to frailty, identified in the pre-period³⁰ • Other comorbidities predictive of hospital emergency admission, as identified in the Inpatient Outpatient A&E and GP(IPOPAEGP) model,³¹ identified in the pre-period

	
 • Number of Elixhauser comorbidities in the pre-period • Number of frailty comorbidities in the pre-period
Support	
 • Resident in a nursing or residential home
Time period	
 • Index date/period (quarter & year, e.g. q1y1, q2y1...)
Level of care available	
 • Locality in which the patient is registered with a GP

All comorbidities will be defined using data from any diagnosis field in any hospital admission in the pre-period.

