It is well known that mental and physical health are interrelated and that when the mental health needs of people with physical health conditions are not adequately addressed, this also negatively impacts on physical health outcomes.^{43,44} People with mental ill health have several times higher rates of A&E attendances, emergency admissions and ACS emergency admissions than those without.⁴⁴ NEHF has included mental health professionals in the

ICTs, providing appropriate care for patients with mental health problems. As a subgroup analysis, sample size permitting, the IAU will identify patients with a history of mental ill health and evaluate the effect of ICTs on the defined outcomes (independent of whether the attendance or admission was primarily for a physical or mental need) on this subgroup. The mental health subset cohort will be classified as those who can be identified in hospital data as having had a diagnosis for mental ill health, that is, those who had at least one inpatient admission or outpatient appointment with a diagnosis of any mental and behavioural disorder (ICD-10, Chapter V, codes F00 to F99),⁴⁵ or, where the main specialty (medical specialty under which the hospital consultant is contracted) was mental health (NHS specialty codes 700 to 715)⁴⁶ within the previous three years. The subset will include those with a serious mental illness, such as schizophrenia, bipolar disorder or psychosis, as well as less severe mental ill health. The definition is similar to that of previous research,⁴⁴ but identifies patients with any diagnosis, whether primary or secondary, while the previous research only included those with a primary diagnosis of mental ill health.

Sensitivity analyses

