The IAU identified a number of ‘overlapping’ in-patient spells (stays) in the SUS data where, for example, a patient spell with one provider did not end before a spell with another provider started. When calculating average length of stay, we did not account for these overlapping spells. Instead, the average length of stay was calculated for each spell, as recorded in the data. Note: For the outcomes emergency bed days and elective bed days, bed days were not double-counted, that is the number of unique days in hospital following either emergency or elective admission were calculated.

Duplicate outpatient appointments were removed. Outpatient appointments relating to mental health services, to the extent these were recorded in the outpatient data, were included.

Index dates and follow-up, page 24

To further limit the size of the dataset of potential controls, only one potential index date per quarter was created for potential patients aged less than 65 years. Only 14% of ICT patients in the study were younger than 65 years.

Baseline variables, page 26

The variables mental ill health and serious mental ill health, as defined on page 32, were included as baseline variables, replacing the mental health definition specified in IPOPAEGP.

Connective tissue disease in the IPOPAEGP was not included as a baseline characteristic, as it overlapped with the Elixhauser definition of rheumatic arthritis. The Elixhauser variable peripheral vascular disorders was not included in error.

Identifying control group, page 28

Due to low numbers of care home residents that were referred to ICTs (<10), matching on type of residence (ie whether a person lived at home, in a nursing or a residential care home) was not done by exact matching.

Matching parameters, page 29

Due to the size of the dataset of potential control patients (approximately 750,000 records), the parameters for the genetic matching algorithm was limited to iterations based on population size 200, maximum generation 100 and number of generations to wait 10.

Statistical analysis, page 30

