Modelling options also included adjusting for only a list of 'core' variables and those variables considered most predictive of the outcome, as the low number of events for some of the outcomes may otherwise have led to over-parametrised models. The most predictive variables were identified by running a lasso regression and where possible included all core variables as a minimum.⁵⁷ Variables considered 'core' were: age; gender (male or not male); IMD quintile; locality; Charlson Index; number of Elixhauser comorbidities; number of frailty comorbidities; history of mental ill health; index date quarter; hospital use in year prior to index date; and emergency admissions, CACS emergency admissions and UCS emergency admissions in the two months prior to index date.

Due to low numbers of care home residents (<10) in both ICT and matched control groups, analyses only adjusted for whether patients lived at home or in a care home (i.e. no differentiation between nursing and residential homes).

Following the analysis, it was found that outpatient appointments included community data from Virgin Care Services that had been uploaded to SUS in error. These appointments were removed from the data and the analysis of outpatient hospital use was redone. Other outcomes were not reanalysed; therefore in the case where these analyses adjusted for outpatient appointments in the year prior to the study, this variable would have contained some community outpatient appointments from Virgin Care Services.

Modelling options did not include multilevel models with locality as a random effect, as five localities were considered too few groups to adequately run such a multilevel model.

Acknowledgements

We are grateful to the North East Hampshire and Farnham CCG team for their support and their review and feedback on an earlier version of this statistical analysis protocol. We are also grateful to [name] and [name] for their peer review comments on an earlier version.

References

- ¹ NEHF CCG. Happy, Healthy, at Home (accessed 29 June 2017). Available from: www.northeasthampshireandfarnhamccg.nhs.uk/about-the-ccg/happy-healthy-at-home
- ² Moran P. Short Stay Emergency Admissions. NEHF CCG, available on request. 2016.

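### A known error in the prior-year outpatient covariate was corrected only for the outpatient outcome, so the adjusted models for the other outcomes probably still use the wrong count, with no recheck of balance

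*Protocol*

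**What the plan says.** The Addendum (Statistical analysis, page 30) describes the error and how far it was corrected. "Following the analysis, it was found that outpatient appointments included community data" from a community provider, loaded into SUS by mistake. "These appointments were removed from the data and the analysis of outpatient hospital use was redone". On everything else it says: "Other outcomes were not reanalysed; therefore in the case where these analyses adjusted for outpatient appointments in the year prior to the study". The consequence it draws for the covariate is that "this variable would have contained some community outpatient appointments".

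The Background (Integrated care teams) explains why these records do not belong: "However, community appointments are not documented in the SUS data".

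Table 3 (Baseline variables) lists "Number of outpatient attendances in year -1 of the pre-period" under prior hospital use, as a potential variable for matching or for adjustment. The Baseline variables section expects all potential covariates to be adjusted for. The reduced models in the Addendum keep prior-year hospital use on the core list, and core variables were included where possible.

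Under Matching parameters, the diagnostics are to cover every baseline variable, and a standardised difference below 10% is cited as negligible. Under Choice of matching variables, only a subset of the variables is expected to enter the algorithm. That subset is not listed.

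The Addendum (Baseline variables, page 26) also discloses a separate slip: "The Elixhauser variable peripheral vascular disorders was not included in error".

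**The concern.** A covariate was found to be wrong and the data were cleaned, but the cleaned data were used for one outcome only. The five primary outcomes (emergency admissions, chronic ACS admissions, urgent care sensitive admissions, A&E attendances and length of stay after emergency admission) keep models that may adjust for the uncleaned count. The outpatient result and the other results then rest on two different versions of the same source file.

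The study relies on matching and regression to make a clinically selected group comparable with controls, and the protocol names unobserved confounding as a main threat. If the stray appointments fall unequally between the groups, adjusting for the contaminated count treats patients with different true outpatient use as alike. Part of that difference then passes into the treatment estimate. Disclosure tells the reader that this may have happened. It does not say in which models, by how much or in which direction.

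**Working it through.** **Scope of the correction.** Study endpoints lists 5 primary and 7 secondary outcomes, 12 in all. One of them, outpatient attendances, was re-run, so 12 − 1 = 11 were not.

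**Do the other models contain the covariate?** The Addendum makes the problem conditional on the model having adjusted for prior-year outpatient appointments. Three statements bear on how often that holds:

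- The Baseline variables section expects adjustment for all potential covariates.
- Table 3 places the outpatient count under prior hospital use.
- The Addendum's reduced models keep prior-year hospital use as core, where possible.

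The core list does not itemise what prior-year hospital use includes. The condition is therefore probably met in most models, but this is not stated.

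**Was the match affected?** Table 3 makes the count a candidate only, the subset used is unlisted, and Table 4 names only type of residence. Matching on the count is neither confirmed nor excluded. If it was a matching variable, the Statistical analysis section would also carry it into the adjusted model.

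**Was balance affected?** Balance was to be assessed on all baseline variables. The balance table should therefore include this count whether or not it was matched on. No recalculation is described.

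**How large could the bias be?** The document gives no number of stray appointments, no split by group and no covariate effect, so there is no figure to reproduce. What follows is an illustration on assumed inputs.

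In a log-linear count model, let b be the log rate ratio per true outpatient appointment and b* the fitted coefficient on the contaminated count. Let Δx be the ICT-minus-control difference in mean true count, and Δc the same difference in mean stray count. With no true effect, approximately:

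log(estimated RR) ≈ b·Δx − b*·(Δx + Δc)

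If Δc = 0 and b* is close to b, this is near zero. If b* = b, it reduces to −b·Δc:

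- Δc = 1: 1/1.01 = 0.990; 1/1.03 = 0.971; 1/1.05 = 0.952
- Δc = 3: 1/1.01³ = 0.971; 1/1.03³ = 0.915; 1/1.05³ = 0.864

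Contamination also weakens b*, which pulls these values back towards 1. A Poisson simulation allows for that. Its assumptions were 200,000 patients per group, true rate ratio 1, mean true count 8 (ICT) against 6 (control), an over-dispersed outcome, and stray appointments with no prognostic value. Rate ratios after adjusting for the contaminated count were:

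| Mean stray appointments, ICT vs control | 1% per appointment | 3% | 5% |
|---|---|---|---|
| 1 vs 1 | 0.99 | 1.00 | 1.01 |
| 2 vs 1 | 0.99 | 0.98 | 0.97 |
| 4 vs 1 | 0.98 | 0.94 | 0.91 |

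Simulation noise is about 0.01; adjusting for the true count gave 0.991 to 1.005. Equal contamination does next to nothing. Unequal contamination produces a spurious benefit if ICT patients carry the excess. By the formula, the sign reverses if controls do.

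**The case against.** The best defence is that the error is disclosed, reaches the other outcomes through one covariate among many, and is harmless if it falls equally on both groups. The protocol already urges caution even for significant results. It also says that the lack of community data hampers control of confounding, so a count that includes some community contact is not necessarily a worse adjuster. All of this stands as a limit on size. It does not justify leaving a known and correctable error in primary-outcome models when the cleaned file exists.

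Several stronger readings are tempting but not supported:

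- *The other outcomes rest on wrong data.* They do not. Admissions, A&E attendances, length of stay, bed days and deaths are not outpatient counts. Unadjusted estimates are touched only if the match was.
- *The match is contaminated.* This would be inferred from silence, because the document does not say that the count was matched on.
- *ICT patients must carry more stray contacts because community matrons sit on the teams.* The covariate covers the year before the index date, which is the first referral, so contact delivered by the ICT falls after it. Community contact before referral could still differ: community staff made 14 of the 84 referrals in January 2017 (14/84 = 17%). The document gives no data on such contact.
- *Residual imbalance far exceeds 10%.* An assumed standard deviation of 6 with 1 to 3 excess contacts gives 1/6 = 17% to 3/6 = 50%. Those inputs are not in the document, and the sum presupposes matching to equality on the count.
- *Missed visits and the mental ill health flag are also wrong.* The flag does cover "those who had at least one inpatient admission or outpatient appointment with a diagnosis of any mental and behavioural disorder", but nothing says that the stray records carried such diagnoses, mental health specialty codes or missed-visit codes. This is a point to check.

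The omitted peripheral vascular variable is a different error, unrelated to the outpatient records.

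**Conclusion.** The point holds in limited form. A covariate known to be wrong was corrected for one outcome of twelve. It probably remains in most of the other adjusted models, including those for the primary outcomes, and balance on the corrected count is not reported. That most models are affected is an inference from the core list and Table 3.

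Size and direction are unknown. On the assumed inputs the effect runs from nothing detectable (0.99 to 1.01) to a spurious rate ratio of about 0.91. The larger figure needs three more stray appointments per ICT patient and a 5% effect per appointment. The document does not show where in that range the study lies, but the data already held can. This should be corrected as well as disclosed.

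**What to change.** 1. Recompute prior-year outpatient attendances from the cleaned file. Check whether any other baseline variable drew on the removed records and, if so, recompute it too.
2. Recalculate the standardised difference of the corrected count in the existing matched sample and report it.
3. Refit every adjusted model that contains the count, with the specification unchanged, and present the corrected estimates beside those already produced. Keeping the specification fixed avoids new modelling choices after the results are known.
4. State which models contain the count and whether it entered the match. If it did, and its corrected standardised difference exceeds 10%, add a re-matched analysis as a sensitivity analysis.
5. Separately, add the omitted peripheral vascular comorbidity to the balance table and to the refitted models. So that the effects of the two corrections can be told apart, show the outpatient correction alone first.

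The cost is some re-running of existing code on data already cleaned, and two sets of estimates to present. A re-match would be heavier, since the search settings were already cut back because of about 750,000 potential control records. It is needed only if both conditions in step 4 are met.
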